**A. PURPOSE OF THE STUDY:**

Determine if an interactive virtual reality (VR) intervention will decrease post-sedation negative behavioral changes one week after ED (emergency department) sedation.

**B. SPECIFIC AIMS/HYPOTHESES**

- 1) Specific Aim: To determine whether a non-pharmacological virtual reality intervention (non-invasive, technology-based distraction via interactive digital game participation) will decrease the incidence of post-sedation negative behavioral changes in children undergoing procedural sedation with IV ketamine in the pediatric ED following their discharge home.
  - i. Hypothesis: Fewer children in the intervention group will have post-sedation negative behavioral changes at 1 week follow up post-discharge as compared to the control group who receive standard of care.
- 2) Secondary Aim: To determine whether administration of a non-pharmacologic virtual reality intervention will decrease anxiety levels just prior to procedural sedation.
  - i. Hypothesis: Children in the virtual reality intervention group will have less anxiety just prior to procedural sedation when compared to controls as evidenced by a reduction in their Modified Yale Preoperative Anxiety Scale (m-YPAS).

**C. BACKGROUND, SIGNIFICANCE, AND RATIONALE**

Procedural Sedation and Outcomes

Pediatric emergency medicine providers administer procedural sedation to minimize patient discomfort and anxiety during diagnostic testing and therapeutic treatments (Kannikeswaran et al., 2017). Institution-specific protocols, individual patient factors, and intended procedures to be performed impact the sedative and analgesic medications administered. Despite highly skilled practitioners and guidelines emphasizing safe and methodical practice, procedural sedations carry risk for adverse effects (Cote et al., 2016). Well-established anesthesia literature of post-operative patients and increasing pediatric emergency medicine literature demonstrates that the adverse effects of anesthesia and procedural sedations are not limited to respiratory, cardiovascular, or gastrointestinal signs and symptoms. Significant and lingering negative behavioral changes can be seen weeks to months post-sedation which have implications for patients and their families that extends beyond the walls of the hospital (Hilly et al., 2015).

Several studies have documented post-operative negative behavioral changes in children following anesthesia and surgery (Eckenhoff 1953, Pearce et al., 2017, Thompson 1993). Investigations have shown that hospitalization and anesthesia can impact children psychologically and behaviorally and contribute to post-operative negative behavioral (PONB) changes (Stargatt et al., 2006, Karling et al., 2006). PONB effects include increased anxiety, sleep disturbance, nightmares, apathy, and eating difficulty (Karling et al., 2005,

Keaney et al., 2004). Children with high anxiety prior to anesthesia or emergency department (ED) procedural sedation are even more vulnerable to develop PONB changes (Beringer et al., 2014, Kain et al., 1996, Kain et al., 1999, Pearce et al., 2018, Zavras et al., 2015). In one study, “very anxious” children were found to be 40% more likely to suffer these changes (Kain et al., 1996).

Children cared for in the ED are subjected to traumatic procedures and stress. It is important that their pain and anxiety are managed appropriately to avoid posttraumatic stress and developing a fear of doctors and hospitals (American Academy of Pediatrics 2006). The new behaviors can additionally have a negative impact on the child’s health, social skills, development, and school work. Therefore, it is important to recognize anxious patients, understand the higher risk for adverse behavioral effects following procedural sedation, and explore remedies for improvement in PONB changes.

#### Risk Factors/Reduction in PONB Changes

A variety of risk factors have been associated with PONB changes. Parental anxiety and younger patient age (Stargatt et al., 2006, Fortier et al., 2010) are associated with increased risk for developing these changes (Hilly et al. 2015). Preexisting somatic conditions, anxiety, depression, and separation anxiety contribute to PONB effects in children (Fortier et al., 2010, Tripi et al., 2004). Children who have frequent temper tantrums are at an increased risk as well as children who have undetected sleep disorders prior to anesthesia and surgery (Tait et al. 2014). Non-white children are at an increased risk for PONB changes (Pearce et al., 2017). Spanish-speaking Hispanic parents reported lower negative behavioral changes in their children compared to English-speaking Caucasian parents, and these findings may be due to a difference in cultural practices and symptom reporting (Fortier et al., 2013).

A host of risk factors for developing PONB changes in pediatric populations following anesthesia or ED procedural sedation have been reported. There are studies primarily in the anesthesia/surgery literature that demonstrate activities that reduce PONB effects. A preoperative preparation workshop for patients and their family showed a reduction in new PONB changes in children and also preoperative anxiety (Hilly et al., 2015). In a double blind-control study, fentanyl given prior to lower abdominal surgery in children undergoing general anesthesia and regional anesthesia exhibited significantly lower negative PONB changes and decreased pain scores (Bortone et al., 2014). A preoperative informational video reduced preoperative anxiety and postoperative negative behavior changes in pediatric patients (Batuman et al., 2016). To our knowledge, similar studies have not been performed in the pediatric ED.

There is some evidence that distraction techniques may help alleviate pre-procedural anxiety and direct attention from the source of pain in certain procedures (Koller and Goldman 2012). Children engaging in medical play and distraction techniques and undergoing difficult procedures in the burn unit experienced less pain and distress (Moore 2015, Khadra et al. 2018). Play therapy as an intervention and the presence of parents reduced anxiety at the induction of anesthesia (Tan and Meakin 2010). Virtual reality has been used as a distraction technique to reduce anxiety and decrease pain (Jones et al., 2016, Mosso-Vazquez et al., 2014, Wiederhold et al., 2014, Gold et al., 2016). For instance, virtual reality which allows children to be immersed in an interactive and simulated world (Sharar and Patterson 2008) has been used in several dental studies to alleviate dental anxiety, and reduce pain associated with procedures (Wiederhold et al., 2014, Aminabadi et al., 2012, Elmore et al., 2016).

Virtual reality interventions have been shown to be well-tolerated by children. Virtual reality because of its immersive nature was used to teach children ages 6 to 12 years with autism spectrum disorder virtual reality safety skills for response to tornado and fire alarms. (Self et al., 2007). Virtual reality technology has been studied with favorable results in decreasing perceived pain via distraction in various pediatric patient clinical scenarios (Dahlquist, et al., 2009) including IV insertion for magnetic resonance imaging (MRI) or computer tomography (CT) (Gold, et al., 2006), burn patients requiring dressing changes (Das, et al., 2005), and oncology patients during port access (Gershon, et al., 2004).

Perceiving pain has a strong psychological component and requires conscious attention to the pain whereas distractions take away some of the attention focused on the pain (Noble et al., 2010). In a randomized controlled trial of 120 healthy children age 4-6 years old, investigators conducted three treatment sessions (Aminabadi et al., 2012). The first consisted of fluoride therapy. In the second treatment one group received restorative treatment without virtual reality eyeglasses and while the third group received therapy with virtual reality glasses. At the end of each treatment, pain was measured with the Wong Baker FACES Pain Rating scale and state anxiety was measured using the Modified Child Anxiety Scale. A significant decrease in both perceived pain and state anxiety was found with the use of virtual reality eyeglasses.

Several clinical benefits have been found using virtual reality. However, a few reports of side effects, such as nausea have been documented in the literature. Aminabadi et al. conducted a clinical trial using 120 children ages 4-6 years old to determine if a virtual reality distraction decreased pain and anxiety during dental procedures. Pain decreased during the restorative procedures and only 2.5% of the children failed to complete the study. Schneider et al. reported children ages 10-17 years old found virtual reality games provided temporary relief from the stress of chemotherapy treatment and nausea was measured in the study. Nausea was rated on a 1 to 5 scale. The average rating by the participants was low at 1.4. In another study, Gold et al. compared standard care to a virtual reality distraction in 20 children age 8 to 12 to determine if pediatric pain decreased during IV placement. Pediatric pain decreased and none of the children experienced simulator sickness (nausea, vomiting, headaches, etc.). The vast majority of patients experience no side effects and complete research investigations. The risk of bad side effects is extremely low due to redesign of the helmets and proper fitting of the devices (Newbutt et al., 2016).

To our knowledge, evaluating the use of a non-pharmacologic, virtual reality intervention and its effects on reducing PONB changes following patient discharge has not been evaluated. Our investigation may improve patient outcome, satisfaction, and experience due to decreased anxiety and PONB changes at home.

#### **D. DESIGN AND METHODS**

[figure not shown]
- Study Design: This is a randomized control trial.
- Site: Children's Hospital of Wisconsin (CHW) ED.
- Subjects: Subjects will be recruited during ED hours when research assistants (or other member of the research team) are available.
  - Inclusion criteria: Children ages 6 years to 17.5 years old receiving procedural sedation with IV ketamine in the CHW ED for long bone fracture reduction. See Appendix A. This age group is most likely to achieve positive effects, fit the VR headset equipment, and tolerate the device without adverse side effects.
  - Exclusion criteria: Patients with moderate to severe developmental delay will be excluded because the anxiety scoring tools have not been validated in this population. Non-English-speaking patients/families will be excluded because the parent survey questionnaire has not been developed and validated in languages other than English. Patients taking psychotropic medications will be excluded because these pharmaceuticals may affect measuring the primary outcome, PONB changes. See Appendix B. Patients with a history of severe motion sickness will be excluded. Patients currently experiencing nausea will be excluded. Patients who have severe visual impairment will be excluded as the VR intervention engages patients in an interactive game that requires navigation through visual content on the VR headset/screen. Patients with an expected admission to the hospital post-procedure will be excluded because outcome data may be affected by this. For a portion of patients this will not be known until after the fact. These patients will be excluded and considered screening failures.
- Demographic Data: The research assistant (or other member of the research team) will collect routine demographic data from the electronic medical record and/or from the patient's parent or guardian including age in years, gender, race, weight in kilograms, medical comorbidities, procedure type and history of sedation difficulty. Additionally, the parent/guardian will be asked to provide their phone number and select the best time of day for the research assistant (or other member of the research team) to call for phone follow-up, cell phone number to text, provide an email address, and mailing address. Parents will be contacted by the research assistant (or other member of the research team) at 1 week follow up via phone, text, email (via secured REDCap link) and/or mail to complete the post-hospitalization behavior questionnaire (PHBQ) and pain survey. One PHBQ survey and pain survey is completed. This information will be collected by the Research Assistants (or other member of the research team) on questionnaires on REDCap or by paper. See Appendix C.
- Measures:
  - Anxiety: To assess the patient's anxiety, the following assessment tool will be used.
    - Modified-Yale Pediatric Anxiety Score (m-YPAS): See Appendix D.

The m-YPAS is a widely used by medical providers to assess patient anxiety at the time of induction of anesthesia. It is designed to be completed in less than 1 minute. It was originally developed for use in children ages 2-6 years but has since been modified to include adolescents. It is reliable and its validity compares favorably to that of the gold standard, the STAI-C (Kain, Z. 1997). The patient's provider (attending physician or fellow physician) will assess the patient's anxiety using the m-YPAS twice during our study: 1st upon patient arrival and enrollment and 2nd immediately preceding sedation after VR intervention or standard of care (depending on which group patient has been randomized to). This will be given to the research assistant (or other member of the research team) to score. The score will not be shared with the physician.

- **Procedure Measures:** Variables that might be associated with the primary outcome will be collected. Following the procedure, charts will be reviewed to collect: 1) the type of pain medication given in the ED, 2) the dose (mg/kg and total number of doses) of pain medication given in the ED, 3) the anxiolytic medication given in the ED, 4) the dose (mg/kg and total number of doses) of anxiolytic medication given in the ED, 5) the type of pain medication prescribed for home, and 6) the dose (mg/kg and total number of doses) of pain medication prescribed for home. See Appendices E and F.
- **Outcome Measures:**
  - **Post-Hospitalization Behavior Questionnaire (PHBQ):** See Appendix F. The PHBQ is a parent-report questionnaire with 27 items in six categories, comprising general anxiety, separation anxiety, sleep anxiety, eating disturbance, aggression towards authority, apathy, and withdrawal. This questionnaire has been used extensively since its development in 1966 to study negative behavioral changes in children post-surgery or hospitalization (Kain et al., 1996, Kain et al., 1999) and was recently used to evaluate the same after minor ED procedures (Brodzinski et al., 2013). This questionnaire takes approximately 10 minutes to finish. This tool will be completed by a parent(s)/guardian(s) prior to the sedation and during phone or mail follow-up post-sedation.

Procedures of the study: The study procedure is outlined in the diagram below (Figure 1).

Figure 1. Procedures of the study

Patients will be identified by trained research assistants (or other member of the research team) and enrollment criteria will be reviewed. Parent/guardian consent will be obtained for all eligible patients. A separate assent form will be completed for patient's aged 7- 13 years. Demographic information will be collected from the parent/guardian.

Patient's anxiety measures using the m-YPAS will be completed at baseline by the patient's medical provider (attending physician or fellow physician). A PHBQ will be completed at baseline by the patient's parent. Patients will then be stratified into high and low anxiety groups based on their baseline m-YPAS score (score of 40 or greater being highly anxious) (Pearce, et al., 2017, Kim, et al., 2012, Kain, et al., 2006) and randomized in blocks of 4 by a computer to either the control or experimental group on a 1:1 ratio. See Figure 1.

The control group will receive standard of care. The experimental group will receive the standard of care in addition to our intervention (interactive VR game while waiting to undergo procedural sedation). This children in the control group receiving standard of care will have access to in room activity including TV distraction if desired, parent support and distraction at bedside, and quiet time like a typical emergency department visit for this type of injury. There would be no active intervention or virtual reality game initiated by the Children's Hospital of Wisconsin staff/Research team in the "Standard of Care" group. Children in the experimental group will receive standard of care as detailed above in addition to the virtual reality game intervention. Additionally, children who choose not to participate in the study and/or terminate the study (which is completely voluntary) early, will receive standard of care and resume their planned emergency department course with the medical team without any change to their healthcare. During the consent/assent process for the study, parents and children will be explained the possible groups they could be allocated to and that this determination is random using a computer software.

Virtual reality, a technology-based distraction device, provides the user with the sense of being present in a virtual environment (Waterworth and Riva, 2014). Distraction techniques can be safe and inexpensive and are commonly used to decrease pain in short invasive medical procedures (Sinha et al. 2006). Virtual reality is a distraction technique in which the participant-computer interface allows the user to interact dynamically using, kinesthetics, visual, auditory, and emotion cues within a computer-generated environment (Aminabadi et al. 2016, Silfer et al., 2002). It uses a head-set, three-dimensional displays, a wide field of view, and motion sensors. Immersive images are placed in front of the eyes of the participant and the headset blocks out outside stimuli as the user interacts with the virtual environment. Since the focus is on what is going on in the virtual world, less attention is focused on the pain or anxiety the patient may be experiencing. The decrease in pain may be due to the virtual reality headset taking attention from the painful stimuli thus taxing the patients limited attention capacity (Wismeijer and Vingerhoets, 2005). We hypothesize that there may also be a decrease in anxiety for these same reasons.

The research assistant, (or other member of the research team) will receive hands-on training from the study investigators per the protocol and device user manual on the operation and use of the VR device and software with the opportunity to use the device as a subject themselves/application onto another individual to ensure competence prior to study enrollment. The research assistant (or other member of the research team) will assist the patients in the VR intervention group by explaining the technology-based distraction device using a standard script provided. See Appendix G. The research assistant (or other member of the research team) will additionally set up the technology system to comfortably fit the patient's head, turn on the VR device, assist the patient in starting the game of their selection, and remove the device when VR intervention has been completed. The headset is thick like a pair of goggles and can be adjusted to fit comfortably on children and to make sure the virtual image is sharp and in focus. Consistent with the procedures used previously by Aminabadi et al., participants will be introduced to virtual reality headset using a tell-show-do technique. The child will be told this is a virtual reality headset and it allows you to play a creative activity or game prior to sedation and this is how to work the headset. It goes on your head and you turn it on and the activity begins. If at any time the child does not wish to continue the activity or game, they will let the research assistant (or other member of the research team) know by raising their hand or saying so. The interactive tell-show-do approach establishes a rapport with the participant, so they are more comfortable and allows time for questions to be answered.

The VR headset, device, and software, created by Stanford's Childhood Anxiety Reduction through Innovation and Technology (CHARIOT)program/Weightless Studio, LLC will be utilized in this study. Patients in the VR intervention group will be allowed to select a distraction-based game to play with active VR content featuring interactive avatars and interactive experiences tailored to the pediatric population that allow players to do things such as control penguins sliding down a mountain while collecting pebbles for points, control puppies running in space to collect treats to the rhythm of music, and control an asteroid miner exploring an asteroid belt and collecting points based on color of asteroids collected, for example. See appendix H.

The game will last a minimum of 5 minutes in duration, provided patient tolerance. The patient may play longer if desired prior to receiving procedural sedation and the total length of activity played will be documented by the RA who will record patient's start and stop time. The VR device will not be applied until the pending time of the procedure is known, such that it will be removed from the participant no longer than 5 minutes before the sedation procedure is initiated, provided patient tolerance. The VR device will be removed when the X-ray technician team arrives to the room prior to the start of the sedation. The time from VR removal to the time of m-YPAS assessment and time of sedation medication administration will be collected and analyzed.

The VR intervention will require the use of the patient's head to navigate the characters in the game (i.e. looking left, right, up or down) and will not require the patient to get out of bed, move their arms, or legs. The research assistant (or other member of the research team) will initiate the VR intervention for patient, record the duration of intervention, and denote any reports of distress including nausea or dizziness (See Appendix I). Parents will be asked to remain at the bedside with the patient throughout the VR intervention, keep the rails of the bed up at all times, push the call light to notify the RA when the child has completed the game, and advocate for their child if the VR experience is poorly tolerated as an additional safety measure.

At the closure of the game the research assistant (or other member of the research team) will remove the headset. The headset will then be thoroughly cleaned with hydrogen peroxide wipes and/or replacement of facemask according to standard infection control recommendations for the CHARIOT VR device before the next study participant's use. See Appendix J.

After intervention and immediately preceding sedation, anxiety measures using m-YPAS will be reassessed by the medical provider (attending physician or fellow physician).

The physician will perform the sedation per CHW ED sedation policy. The sedation will be administered and as appropriate the patient discharged. Child life consultation by nursing staff or medical provider as an adjunct to patient care during ED course will be permitted per standard procedure and noted. See Appendix K.

Follow-up with the family will be performed by the research assistants (or other member of the research team) between 7-14 days after ED discharge consistent the procedures followed previously (Pearce et al., 2017). Phone, secured REDCap email/text, and mail surveys will be sent. One PHBQ and pain survey will complete the study. Follow up contact via email/text will include instructions for the parent to complete the PHBQ survey and pain questions via a link that will be provided through the secured REDCap database and record their responses electronically. Script content will be consistent with the example documented in Appendix L. The phone follow-up attempts will take place during the hours agreed upon by the parent(s)/guardian(s). The phone follow-up attempts will occur no more than two times per day during the follow-up period. During the phone, email, text or mail follow-up, the PHBQ post-sedation will be administered to assess the degree of change PONB changes post-sedation as well as 3 additional questions regarding post-discharge pain treatment: (1) Was your child prescribed an opiate medication (ie. oxycodone) prescription for pain control at home? (2) Did you fill this prescription? (3) Have you given your child an opiate medication for the pain following discharge from the ED? This phone survey was utilized in a prior study and took no longer than 5 minutes to complete. If the parent(s)/guardian(s) are not reachable by phone after the period specified above, then a paper copy of the follow-up survey will be mailed to him/her along with a self-addressed stamped envelope for return of the survey.

In anticipation of funding, a gift card in the amount of 25.00 will be provided to the child if their parent/guardian completes the study's follow up 1-week PHBQ, our primary outcome of interest. The Research Assistant will track study completion via REDCap and mail receipt of the PHBQ. The gift card will be provided within 1 week of receiving the survey results either via email or mail with the contact information provided upon study enrollment. If the parent/guardian does not complete the 1-week follow up survey, a gift card will not be sent. This incentive will be described to study participant and their parent/guardian at the time of enrollment and detailed in the assent/consent forms.

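### Children whose admission emerges after sedation are already randomised, yet the plan drops them as screening failures, with no count by arm and no exception for the pre-sedation anxiety outcome

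*Combined protocol and SAP*

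**What the plan says.** Section D, exclusion criteria, gives the reason for the rule: "Patients with an expected admission to the hospital post-procedure will be excluded because outcome data may be affected by this". It then deals with admissions that were not foreseen: "For a portion of patients this will not be known until after the fact. These patients will be excluded and considered screening failures".

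The procedures in section D set the order of events. After consent and the baseline m-YPAS and PHBQ, children are stratified by anxiety and "randomized in blocks of 4 by a computer to either the control or experimental group on a 1:1 ratio". VR or standard care follows. Then: "After intervention and immediately preceding sedation, anxiety measures using m-YPAS will be reassessed by the medical provider". Sedation and disposition come last: "The sedation will be administered and as appropriate the patient discharged".

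Section B places Aim 1 in "children undergoing procedural sedation with IV ketamine in the pediatric ED following their discharge home". The hypothesis for the secondary aim has no such limit: "Children in the virtual reality intervention group will have less anxiety just prior to procedural sedation when compared to controls".

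Section O compares two groups for each aim and names no analysis population. Its multiple imputation is for items. Section E asks for 243 children and allows 20% dropout, without saying where later admissions fall.

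**The concern.** A screening failure is a child who never enters the randomised comparison. A child who has been allocated, managed in an arm and sedated is not one, and the label lets such a child leave the randomised denominator unseen. Removal depends on an event after allocation that the plan itself expects to be related to the outcome. If admissions differed by arm, the children left for Aim 1 would no longer be comparable by virtue of randomisation. Without counts by arm, a reader could not tell balanced removal from unbalanced removal.

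The exclusion is also not confined to the PHBQ. Read literally, it takes these children out of Aim 2 as well, although that outcome is complete before sedation starts.

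**Working it through.** **Order of events (section D).** Consent; baseline m-YPAS and PHBQ; randomisation; VR or standard care; second m-YPAS; sedation; discharge as appropriate. An admission learned before randomisation is a true screening failure. One that emerges after sedation concerns a randomised child who normally has both m-YPAS scores. The documents do not say how the late-known cases divide between the two.

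**Does the stated reason apply?** For the PHBQ, collected after the child leaves, yes: a hospital stay may change the answers, and Aim 1 concerns children who went home. For the second m-YPAS, no: it precedes sedation.

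**The plan's own sample size (section E).** Inputs: 25% vs 10%, alpha 0.05 (two-sided assumed), 80% power, 20% dropout. Unpooled formula: (1.960 + 0.842)² × (0.25×0.75 + 0.10×0.90) / 0.15² = 96.8, so 97 per arm. 194 / 0.8 = 242.5, so 243. The plan's figures reproduce. There is almost no slack: 243 × 0.8 = 194.4 against 194.

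The documents give no admission rate, so every rate below is an assumption. Power and false-positive rates are exact, for the uncorrected two-sided chi-square test.

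**Possible bias in Aim 1, no true effect, 25% in both arms.** Rate among the children kept = (0.25 − a·e)/(1 − a), where a is the share admitted and e the event rate among the admitted. Numbers per arm = floor(243 × (1 − a) × 0.8 / 2).

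| a, control / VR | e | Kept, control / VR | Spurious gap | n, control / VR | False-positive rate |
|---|---|---|---|---|---|
| 2% / 1% | 50% | 24.5% / 24.7% | 0.3 points | 95 / 96 | 5.0% |
| 8% / 4% | 50% | 22.8% / 24.0% | 1.1 points | 89 / 93 | 5.4% |
| 10% / 5% | 60% | 21.1% / 23.2% | 2.0 points | 87 / 92 | 6.1% |

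Gaps are taken before rounding. With no exclusion (97 per arm) the false-positive rate is 5.1%. In these rows more control children are removed and the gap leans against VR. With the arms swapped it would favour VR. Equal removal of similar children gives no gap.

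**Power for 25% vs 10%, at 2% / 5% admitted in each arm.**
- Excluded and replaced (97 per arm): 80.2% / 80.2%. This means randomising 243/0.98 = 248 or 243/0.95 = 256.
- Excluded, not replaced, on top of the 20% dropout (95 / 92 per arm): 79.2% / 77.7%.
- All randomised children kept (97 per arm), with 50% events among admitted controls and rate r among admitted VR children. The arm rates are (1 − a)×0.25 + a×0.50 and (1 − a)×0.10 + a×r:
  - r = 50% (no VR effect in the admitted): 77.3% / 72.8%
  - r = 35% (same 15 points): 79.3% / 77.9%
  - r = 20% (same ratio): 81.2% / 82.5%

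The r at which keeping and excluding give equal power depends on the comparison. Against exclusion without replacement it is 0.351 / 0.355, about 35%. Against exclusion with replacement (80.2%) it is 0.276 / 0.277, about 28%.

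**Aim 2.** 2%, 5% or 10% of 243 is about 5, 12 or 24 children. With a two-sample t-test, 80% power and both scores on every randomised child, n per arm is floor(121.5 × (1 − a)) = 119, 115 or 109, against 121 with nobody removed. The detectable difference rises from 0.362 SD to 0.365, 0.371 or 0.381 SD.

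**The case against.** The strongest reply is that the rule defines a target population. Aim 1 asks about behaviour after going home, and the plan gives its reason for leaving admitted children out. That stands for the PHBQ. A reader might infer that an all-randomised PHBQ analysis has to be primary. The documents do not support this: it would answer a broader question than Aim 1 poses, and would lose power if VR works less well in admitted children.

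The numbers are also modest, even though each bias scenario assumes that VR halves admissions and that 50% to 60% of admitted children have events. That stands. The loss of power is not certain either. Screening failures do not ordinarily count towards a target, and if these children are replaced or fall within the 20% dropout, 97 per arm is intact. The gap is that section E does not say which applies.

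A reader might infer that the plan discards the m-YPAS scores. It does not say so, and its stated reason does not reach a pre-sedation score. What stands is that the exclusion is written without limit, so the point needs a clarifying sentence.

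Finally, Figure 1 and the appendices are not visible. The missing counts and analysis set are confirmed only for the readable text.

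**Conclusion.** The point holds as a gap in labelling, reporting and analysis sets. For admissions that emerge after sedation, the rule is a post-randomisation exclusion under the wrong name, and its stated reason cannot cover Aim 2. Admissions known before randomisation are properly screening failures.

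A reader might infer that the rule biases the trial towards VR. The documents do not support this: nothing in them links arm to admission or gives an admission rate, so neither the presence nor the direction of bias can be established. Under the assumed rates the effect on Aim 1 is at most 2.0 points, with a false-positive rate of 6.1% against 5.1%, and the Aim 2 loss is at most about 0.02 SD. Severity is minor to moderate: the effect is probably small, but it cannot be checked under the current text.

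**What to change.** 1. In section D, limit the screening-failure label to admissions known before randomisation.
2. Keep every randomised child with both m-YPAS scores in the Aim 2 analysis, in the assigned arm.
3. Count later admissions and report them by arm as post-randomisation exclusions from the discharged-children analysis.
4. Seek the PHBQ from these children in a window counted from the date of ED sedation. Section A times the outcome from sedation, while section D counts 7 to 14 days from ED discharge, which is unclear for an admitted child. In section O, keep discharged children as the primary Aim 1 population and prespecify an all-randomised PHBQ sensitivity analysis.
5. In section E, state whether later admissions are replaced or fall within the 20% dropout. Replacement at an assumed 2% or 5% would mean randomising about 248 or 256.

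Items 1 to 3 are wording and reporting changes and cost no power. Item 4 costs a few follow-up contacts and one added analysis, in which some PHBQ answers will reflect a hospital stay. That is acceptable in a sensitivity analysis and should be said when it is reported.
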